The biggest caution should be given to upper gastrointestinal haemorrhage and perforation associated with peptic ulcer of all the gastrointestinal mucosal disorders caused by NSAID. The US national survey showed that 13 of 1,000 patients with rheumatoid arthritis who had taken NSAID for one year and 7.3 of 1,000 patients with osteoarthritis developed severe gastrointestinal complications, which suggests that at least 16,500 patients with rheumatoid arthritis or osteoarthritis per year would die in such complications ([Singh G, et al., 1999](#)). According to the recent Japanese epidemiological survey on upper gastrointestinal haemorrhage, the result from a case control study in the general population reported 5.8-fold higher risk of upper gastrointestinal haemorrhage in patients treated with NSAID including low-dosed aspirin ([Sakamoto C, et al., 2005](#)), compared to those not treated with NSAID. There is another report that approximately 30% of patients who were hospitalised due to haemorrhage associated with peptic ulcer have NSAID-associated peptic ulcer ([Nakashima S, et al., 2005](#)). Given the fact that NSAID-associated peptic ulcer is often asymptomatic ([Shiokawa Y, et al., 1991](#)), however, it is not easy to predict occurrence of peptic ulcer, judging from subjective symptoms. These reports suggest that appropriate preventive measures should be taken for patients on NSAID.

The use of NSAID is recommended as the first line therapy for the treatment of rheumatoid arthritis ([The Manual for Diagnosis and Treatment of Rheumatoid Arthritis](#)). Meanwhile, the following measures may reduce the risk of occurrence of peptic ulcer in patients on NSAID: (1) medication is switched to another drug with lower risks, (2) anti-peptic ulcer agent is given to prevent occurrence of gastrointestinal mucosal disorders. Selective COX-2 inhibitors are

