3.3.5 Discontinuation of subjects from study treatment or assessment

3.3.5.1 Criteria for discontinuation

Subjects may be discontinued from study treatment and assessments at any time.

Specific reasons for discontinuing a subject from this study are:

- Voluntary discontinuation by the subject who is at any time free to discontinue his/her participation in the study, without prejudice to further treatment
- Safety reasons as judged as the patient to be discontinued by the investigator(s) and/or AstraZeneca K.K.
- Severe non-compliance to protocol as judged by the investigator(s) and/or AstraZeneca K.K.
- Incorrect enrolment i.e., the subject does not meet the required inclusion/exclusion criteria for the study
- Subject lost to follow-up
- Occurrence of an event in conflict of exclusion criteria (e.g., pregnancy)
- Development of gastric and/or duodenal ulcer
- Difficulty to conduct the study as judged by the investigator(s) due to the presence of gastric and/or duodenal mucosal lesion such as bleeding.
- Permanently stopping treatment with daily NSAID
- Others as judged appropriate by the investigator(s) (reasons for discontinuation must be recorded in eCRF)

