4.6.1 Presence/Absence of gastric and/or duodenal ulcer

4.6.1.1 Methods of assessment

At Visits 1, 3, 5, 8 and 15 (at screening, Weeks 4, 12, 24 and 52 after initial administration), EGD will be performed in the fasting state to confirm presence/absence of gastric and/or

duodenal ulcer based on the following criteria. If gastric and/or duodenal ulcer is present, the site, stage (the Sakita/Miwa classification) and longitudinal diameter of ulcer will be recorded in the eCRF.

Presence/Absence of gastric and/or duodenal ulcer

If gastric and/or duodenal ulcer is verified by EGD and is in the active stage (A1 or A2) or in the healing stage (H1 or H2) according to the Sakita/Miwa classification, “presence of ulcer” should be defined.

Site of ulcers:

Site I: cardia part, fornix, upper gastric corpus, middle gastric corpus, lower gastric corpus, gastric angle, pyloric vestibular part, bulb, retrobulbar region

Site II: anterior wall, posterior wall, greater curvature, lesser curvature

Stage (Sakita/Miwa classification)

Active stage:

A1: Slough in the ulcer is thick with inflammatory swelling in the marginal area.

A2: Circumferential white ring and hyperemia are seen in the marginal area of the ulcer.

Healing stage:

H1: The ulcer is shrunk with redness in the marginal area, and mucosal plicae are gathering.

H2: The ulcer is further healed and upheaved, being covered with thin slough

Scar stage:

S1: so-called ‘Red Scar’: Hyperemia still remains in the centre of the scar.

S2: so-called ‘White Scar’: Hyperemia in the scar disappears, turning into the same colour as adjacent mucosa.

The longitudinal diameter

The longitudinal diameter will be measured referring such as endoscopy forceps. If several ulcers are found, record the longitudinal diameter of the largest ulcer.

EGD images

For the central review of confirmation about presence/absence of gastric and/or duodenal ulcer, EGD images showing the sites judged to be the scar of ulcers at screening and the sites

judged to be the ulcers during the treatment period with the investigational product (one each of close and distant views. The same is required for EGD images in the past used for a lesion with unclear scar) will be submitted to AstraZeneca K.K.. The personal information (such as the name and the medical record number) which can specify the patient should be masked before submission to AstraZeneca K.K..

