6.4.2.1 Gastric and/or duodenal ulcer free status

The following two methods will be used to calculate each proportion of subjects without gastric and/or duodenal ulcer (ulcer-free rate) in FAS and PPS. The population excluding subjects who are declared not to have an ulcer scar by the central evaluation committee at baseline will be evaluated (see Section 6.7). In this analysis, the evaluation of the central committee for the presence/absence of gastric and/or duodenal ulcer after dosing will be used.

[Ulcer-free rate by the Kaplan-Meier method]

It will be defined as an event if gastric and/or duodenal ulcer is observed by EGD and the plots to show the period from the date of initial administration to the date of event occurred will be constructed using the Kaplan-Meier method. Data obtained from the subjects who have not developed ulcer throughout the study period will be cut off on the day of the last test with EGD. Ulcer free rates of gastric and/or and duodenal ulcer at Week 4, 12, 24 and 52 and its 95% confidence intervals will be calculated by the constructed Kaplan-Meier plots.

[Ulcer-free rate by EGD performed at each measurement]

Subjects who remained gastric and/or duodenal ulcer-free status confirmed by the EGD at Weeks 4, 12, 24 and 52 after the initial administration or those who discontinued the study by reason that gastric and/or duodenal ulcer-free status was confirmed before performing the EGD at each measurement will be considered as ulcer-free subjects and the proportion of the ulcer-free subjects will be calculated against the entire number of the subjects included in the

analysis population, and its 95% confidence intervals will be calculated. The proportion of the ulcer-free subjects will be stratified by the following factors to calculate the percentages for each subgroup.

- Sex (Male, Female)
- Age (<65, 65-74, 75≤)
- Hp positive/negative
- Number of types of NSAID (one or more types)
- Use of steroidal agent(s) (Yes or No)
- Genotypes of CYP2C19 (homo EM, hetero EM, PM)
- Underlying diseases (e.g., osteoarthritis, rheumatoid arthritis, lumbago)
- Degree of gastric mucosa atrophy (positive or negative)
Positive: Concentration of pepsinogen I is 70.0 ng/mL or below and pepsinogen I/II is 3.0 or below
Negative: Concentration of pepsinogen I is 70.1 ng/mL or above or pepsinogen I/II is 3.1 or above
- Extension of gastric mucosa atrophy (no atrophy, C-1, C-2, C-3, O-1, O-2, O-3)

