6.7 Central evaluation committee

For this study, a central evaluation committee that consists of experts in gastroenterology will be established to confirm the rationale for judgement by the investigator(s) based on the EGD.

The board will review the findings of the baseline EGD that was judged as the scar of ulcer and EGD images taken before screening and used for eligibility assessment due to unclear scar at baseline, and EGD images by which the investigator(s) confirmed gastric and/or duodenal ulcer after initial administration as needed, and report the results of the review to AstraZeneca K.K..

Time to hold the meeting and the responsibilities of the board members will be determined separately.

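### The ulcer-free rate counts only ulcers seen by EGD and evaluated by an image-based committee, so an ulcer documented in any other way has no route into it

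*Protocol*

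**What the plan says.** Protocol section 6.4.2.1 estimates the ulcer-free rate by Kaplan-Meier and, separately, at each EGD time point.

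- **Kaplan-Meier event:** "It will be defined as an event if gastric and/or duodenal ulcer is observed by EGD". No other route of diagnosis is named.
- **Whose reading counts, for both rates:** "the evaluation of the central committee for the presence/absence of gastric and/or duodenal ulcer after dosing will be used".
- **What the committee reviews after dosing (section 6.7):** "EGD images by which the investigator(s) confirmed gastric and/or duodenal ulcer after initial administration as needed". Section 4.6.1.1 defines presence of an ulcer as one verified by EGD in an active or healing stage, and asks sites to send one close and one distant view.
- **Censoring:** "Data obtained from the subjects who have not developed ulcer throughout the study period will be cut off on the day of the last test". The test meant is the EGD.
- **Visit-based rate:** besides subjects clear at the EGD in question, a hard-to-parse clause also counts as ulcer-free those who left the study with ulcer-free status confirmed before that EGD.

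Elsewhere, section 3.3.5.1 lists "Development of gastric and/or duodenal ulcer" as a reason for discontinuation without naming a method of diagnosis. Section 4.7.1.1 makes an event that is fatal, life-threatening or requires admission an SAE. Table 2 schedules EGD at screening and at Weeks 4, 12, 24 and 52. Its footnote k asks for the Week 52 tests at early discontinuation, but only as far as feasible.

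**The concern.** Section 1.1.2 names the outcomes that matter most: "The biggest caution should be given to upper gastrointestinal haemorrhage and perforation associated with peptic ulcer". These are also the outcomes most likely to come to light between scheduled EGDs, in an emergency and possibly without endoscopy. The longest stretch without a planned EGD is the 28 weeks from Week 24 to Week 52.

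Consider a subject with a clear Week 24 EGD who is admitted at Week 40 with a perforated ulcer found at surgery, and who has no later EGD. The safety tables show a serious ulcer. The efficacy tables show no ulcer event. The two parts of the report then disagree about the same subject, and the efficacy side errs towards a better ulcer-free rate. Under section 6.6, both the 24-week and the 52-week results go to the authority for the approval application.

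**Working it through.** The plan states no figure for this point. The check is first of wording, then of size.

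**Following the Week 40 subject through the rules**

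1. *Kaplan-Meier event?* No. The ulcer was not observed by EGD, and the committee has no image to evaluate.
2. *Kaplan-Meier censoring?* Not clearly. The rule is worded for subjects who have not developed an ulcer, and this subject has. No third category exists, so the likely handling is that the data "will be cut off on the day of the last test with EGD", here Week 24.
3. *Visit-based rate at Week 52?* The subject discontinued, and the last confirmed status was ulcer-free. The clause for discontinued subjects is unclear, but it does not exclude this subject, who could be counted as ulcer-free.
4. *Any other route?* None. No section carries an ulcer recorded as an SAE or as the discontinuation reason into the efficacy event.

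An ulcer seen by EGD without images reaching the committee meets the first condition (observed by EGD) but not the second (evaluated by the committee). The text does not say which prevails.

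**Size per omitted subject**

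With N = 130 (section 6.5), one subject in the visit-based rate is 1/130 = 0.77 points.

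For Kaplan-Meier, assume for illustration 7 committee-read ulcers (2, 2, 1 and 2 at Weeks 4, 12, 24 and 52), no other dropout, and one further ulcer at Week 40:

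- Cut off at Week 24: 128/130 × 126/128 × 125/126 × 122/124 = 125/130 × 122/124 = 94.60%.
- Counted as an event: 125/130 × 124/125 × 122/124 = 122/130 = 93.85%.
- Difference: 0.75 points.

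**How many such subjects**

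Section 1.1.2 gives severe gastrointestinal complications per year of NSAID use as 7.3 per 1,000 (osteoarthritis) and 13 per 1,000 (rheumatoid arthritis).

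- Expected in 130 subjects: 130 × 0.0073 = 0.95 and 130 × 0.013 = 1.69.
- Chance of at least one: 1 − (1 − 0.0073)^130 = 61% and 1 − (1 − 0.013)^130 = 82%.
- Shift if none is captured by EGD: 0.95/130 = 0.73 and 1.69/130 = 1.30 points. If half are captured: about 0.4 to 0.65 points.

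**Against the precision of the estimate**

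Table 1 gives 5.3% ulcers in six months on 20 mg in one overseas study. Assuming constant hazard:

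- Week 52 rate: 1 − (1 − 0.053)² = 10.3%, or 13.4 of 130 subjects.
- Standard error: √(0.103 × 0.897 / 130) = 2.67 points.
- Shift with none captured: 0.73/2.67 = 0.27 SE to 1.30/2.67 = 0.49 SE, equal to 7% to 13% of the expected ulcers (0.95/13.4 and 1.69/13.4).
- Shift with half captured: about 0.14 to 0.24 SE.

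**The case against.** The best case against the point is that an endoscopic endpoint is a coherent choice, used consistently in sections 3.1, 4.6.1.1 and 6.4.2.1. On this view, handling a rare ulcer without EGD belongs in the SAP or the committee's own rules, which section 6.7 leaves to be settled separately. The endpoint is secondary, the study is single-arm and descriptive, and no test or sample size depends on it. A perforation or fatal bleed is an SAE and appears in the primary safety analysis, so it is not lost from the report.

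Much of this stands and limits the weight of the point. It does not remove it. Section 6.4.2.1 does not leave the event open: it fixes a rule, and that rule leaves out true ulcers in one direction only.

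Three stronger readings are tempting, and the protocol does not support them:

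- *That it holds two contradictory definitions of an ulcer.* Section 3.3.5.1 merely names no method. Section 4.7.1.2(b), on when an ulcer is recorded as an AE, speaks of EGD findings, so it cannot be cited as a definition that needs no EGD.
- *That ulcers found at emergency endoscopy are excluded.* The event is not restricted to scheduled EGDs. An unscheduled EGD whose images are available already counts.
- *That the Kaplan-Meier rule expressly censors such a subject as ulcer-free.* It covers only subjects without an ulcer, so the case is unassigned. Being censored is also not the same as being scored a success.

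Footnote k narrows the gap further but does not guarantee an EGD, and it cannot help after a death.

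**Conclusion.** The point holds in a narrow form. An ulcer documented without EGD, or by an EGD whose images do not reach the committee, has no stated route into the ulcer-free rate, even when the study has recorded it as an SAE or as the reason for stopping. Any resulting error raises the rate.

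The size is about 0.77 points per omitted subject at N = 130, and somewhat more if the analysed population is smaller. Few such subjects are expected. The figure of 0.95 to 1.69 is an upper-end illustration: it takes all severe gastrointestinal complications in general NSAID users and assumes that EGD captures none of them. Treatment with the study drug would lower the number, and the ulcer history required for entry would raise it. The documents do not give the net figure. Even at the upper end the shift is about half a standard error. No hypothesis test, sample size or primary safety result is affected. What is at stake is that the most serious ulcers are the ones the efficacy estimate may miss.

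**What to change.** - **Section 6.4.2.1, event:** count any gastric or duodenal ulcer documented after initial administration by EGD, surgery, imaging or autopsy, including a perforated or bleeding ulcer, as an event on its diagnosis date. Apply the cut-off at the last EGD only to subjects with no ulcer documented by any of these routes.
- **Section 6.4.2.1, visit-based rate:** score such a subject as not ulcer-free at that and every later time point, and reword the clause on discontinued subjects so that it cannot include them.
- **Section 6.7:** where EGD images are lacking, let the existing committee adjudicate from the SAE documents, and state whose diagnosis stands if it cannot decide.
- **Sensitivity analysis:** report the EGD-only rate alongside, so that the purely endoscopic result stays visible.

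The cost is a few sentences. The committee exists and SAE information is already collected. The downside is a slightly less favourable ulcer-free rate and a few cases judged without images.

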- j All SAEs and AEs resulted in the subject’s withdrawal that occurred from the time when informed consent was obtained will be recorded in the eCRF. For AEs other than SAEs and AEs resulted in the subject’s withdrawal, only those occurring from initial administration to the last scheduled visit or withdrawal will be recorded in the eCRF.

- k If the subject discontinues the study before completing the treatment period (52 weeks), the subject should undergo the tests planned for Visit 15 (Week 52) as much as possible.
- l Only a haematology test should be conducted (See Section [4.7.2](#) for details.)
- m If these tests were missed at screening, they can be done at any visit until discontinuation/completion of the study.
- n Test data obtained before informed consent can be used with the consent of the subjects, if the test was conducted within 2 weeks prior to the registration.

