4.6.2 Severity of gastric mucosal lesions

4.6.2.1 Methods of assessment

At Visits 1, 3, 5, 8 and 15 (at screening, Weeks 4, 12, 24 and 52 after initial administration), EGD will be performed to evaluate the severity of gastric mucosal lesions (erosion, haemorrhage) by modified LANZA score.

Modified LANZA Score:

- 0: Absence of haemorrhage and erosion
- +1: One haemorrhage or erosion
- +2: 2-10 haemorrhage or erosion
- +3: 11-25 haemorrhages or erosion
- +4: > 25 haemorrhage or erosion or an ulcer

4.6.3 Presence/absence and severity of NSAID-associated GI symptoms (assessment by investigator(s))

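### Subjects withdrawn for a mucosal lesion short of an ulcer are censored in the Kaplan-Meier ulcer-free rate; if their later ulcer risk is raised, the rate is modestly too high, and no planned analysis bounds this

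*Protocol*

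**What the plan says.** - **Event.** Section 6.4.2.1: "It will be defined as an event if gastric and/or duodenal ulcer is observed by EGD". Section 4.6.1.1 limits an ulcer to the active or healing stages of the Sakita/Miwa classification ("If gastric and/or duodenal ulcer is verified by EGD and is in the active stage (A1 or A2) or in the healing stage"), so erosion or haemorrhage alone does not qualify.
- **Censoring.** Section 6.4.2.1: "Data obtained from the subjects who have not developed ulcer throughout the study period will be cut off on the day of the last test", meaning the last EGD. There is no exception by reason for leaving.
- **Withdrawal.** Section 3.3.5.1 lists ulcer development as one reason for discontinuation and, separately, "Difficulty to conduct the study as judged by the investigator(s) due to the presence of gastric and/or duodenal mucosal lesion such as bleeding".
- **Severity scale.** In section 4.6.2.1 the top modified LANZA grade covers "> 25 haemorrhage or erosion or an ulcer".
- **EGD on leaving.** Footnote k to Table 2 (section 3.1): "If the subject discontinues the study before completing the treatment period (52 weeks), the subject should undergo the tests planned for Visit 15", as far as possible. Those tests include an EGD.
- **Adverse events.** Section 4.7.1.2(b) keeps EGD findings out of the adverse event record unless they are serious or lead to withdrawal for a reason other than ulcer. Section 6.4.1(a) tabulates adverse events that led to withdrawal.
- **Status of the analysis.** Efficacy is a secondary objective (section 2.2) and all analysis is descriptive (section 6.1).

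**The concern.** Kaplan-Meier assumes that a censored subject has the same later risk as those still under observation. A subject who leaves because of bleeding or erosions leaves because of damage to the organ in which the event would occur, so that assumption is doubtful. The decision rests on the investigator's judgement in an open-label study with no control arm in which the same process could be seen.

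For any excess risk the error runs in the drug's favour, and it grows with use of the criterion. The ulcer-free rates and their 95% confidence intervals are to be reported, and the 24-week and 52-week results go to the authority (section 6.6).

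Other provisions do not remove the problem:

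- The per-visit rate in section 6.4.2.1 treats as ulcer-free "those who discontinued the study by reason that gastric and/or duodenal ulcer-free status was confirmed before performing the EGD at each measurement". The wording is unclear. One reading makes lesion withdrawals successes, and no reading makes them ulcer cases.
- The on-treatment images sent for central review are those of sites the investigator judged to be ulcers (sections 4.6.1.1 and 6.7). A lesion judged not to be an ulcer is not routinely reviewed.
- The LANZA summaries are made by time point, and a withdrawn subject contributes nothing afterwards.

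**Working it through.** The protocol states no expected ulcer-free rate, number of lesion withdrawals or excess risk, so there is no planned figure to reproduce. The calculation below is an illustration.

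**Inputs**
- n = 130 (section 6.5).
- Ulcer incidence on 20 mg: 5.3% at 6 months (Table 1, SH-NEN-0014), taken as 26 weeks.
- Assumed: a constant hazard; m = 3 or 6 subjects withdrawn ulcer-free after the EGD at Week 4, 12 or 24; and k = 1, 3 or 10 times the hazard afterwards. There is no other dropout.

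**Formulas**
- Hazard: h = −ln(1 − 0.053)/26 = 0.002094 per week.
- Expected Kaplan-Meier rate under the protocol's rule: S(52) = exp(−52h) = 0.947² = 0.897, a risk of 10.3% or about 13 of 130. It does not depend on m or k.
- Let w be the withdrawal week, S(w) = exp(−hw) and f = m/(130·S(w)).
- True rate: S(w)·[(1 − f)·exp(−h(52 − w)) + f·exp(−kh(52 − w))].
- Withdrawals counted as events: S(w)·(1 − f)·exp(−h(52 − w)).

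**One case in full (w = 4, m = 6, k = 10)**
- S(4) = 0.9917, so 128.9 are at risk and f = 6/128.9 = 0.0465.
- exp(−48h) = 0.9044 and exp(−480h) = 0.3659.
- True rate: 0.9917 × (0.9535 × 0.9044 + 0.0465 × 0.3659) = 87.2%.
- Overstatement: 89.7 − 87.2 = 2.5 points.
- Counted as events: 0.9917 × 0.9535 × 0.9044 = 85.5%.

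**Results at Week 52 (protocol rule 89.7% throughout; ranges over withdrawal at Week 24 to Week 4)**

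| m | k | True rate | Overstatement (points) |
|---|---|---|---|
| 3 or 6 | 1 | 89.7% | 0 |
| 3 | 3 | 89.4–89.3% | 0.24–0.38 |
| 3 | 10 | 88.8–88.4% | 0.89–1.24 |
| 6 | 3 | 89.2–88.9% | 0.48–0.76 |
| 6 | 10 | 87.9–87.2% | 1.78–2.49 |

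The overstatement is taken from unrounded rates. Subtracting the one-decimal rates gives 0.3 to 1.3 points for m = 3 and 0.5 to 2.5 for m = 6.

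**Worst-case bound (every lesion withdrawal a failure)**
- Crude: 117/130 = 90.0%, against 114/130 = 87.7% for m = 3 and 111/130 = 85.4% for m = 6. The differences are 3/130 = 2.3 and 6/130 = 4.6 points.
- Same model as above: 87.5–87.6% for m = 3 and 85.3–85.5% for m = 6, which is 2.1–2.2 and 4.2–4.4 points below 89.7%.

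**Scale.** The 95% half-width for a rate of 90% with 130 subjects is 1.96 × √(0.9 × 0.1/130) = 5.2 points.

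**The case against.** **The effect is small and its inputs are unknown.** This stands. In all the cases shown the overstatement is less than half the confidence interval's half-width. Unlike sampling error, though, it has a known direction.

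**A discontinuation EGD is requested.** This stands in part. An ulcer already present at withdrawal will usually be found and counted. Only ulcers that would have developed later are lost.

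**The withdrawals are already recorded.** This also stands in part. Under sections 4.7.1.2(b) and 6.4.1(a) they should appear among adverse events leading to withdrawal. That shows how many there were, but does not link them to the ulcer-free rate.

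**Raised risk is not demonstrated.** A reader might infer from the shared top LANZA grade ("4: > 25 haemorrhage or erosion or an ulcer") that these subjects are known to be close to ulceration. The protocol does not support that: the withdrawal criterion is not tied to any LANZA grade, a single haemorrhage scores only +1, and sharing a severity grade says nothing about later hazard. Raised risk is plausible, no more.

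**Counting them as events changes the endpoint.** Correct. A reader might take the 2.3 to 4.6 points as the bias. It is the gap between two endpoints, and would equal the bias only if every such subject would have developed an ulcer by Week 52.

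**The detail belongs in the SAP.** A sensitivity analysis could be placed there. The event and censoring rules, however, are fixed in the protocol, so the point can be raised against it.

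**Conclusion.** The concern holds in a limited form. Section 6.4.2.1 censors lesion withdrawals as if they were at average ulcer risk, and no analysis in the protocol shows how much this matters. With a 52-week risk of about 10% and 130 subjects, the ulcer-free rate is overstated by about 0.2 to 1.2 points for 3 withdrawals and 0.5 to 2.5 points for 6, at 3 to 10 times the hazard. At average risk there is no bias. The worst-case bound is about 2.3 to 4.6 points. The counts, the hazard ratios and the extrapolation from 6 months to 52 weeks are all assumptions.

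A reader might conclude that the trial's main result is compromised. It is not: the primary objective is safety, the ulcer-free rate is a secondary descriptive result and no hypothesis is tested. Section 6.4.2.1 gives two ulcer-free rates without naming either as the main one, and section 1.2 refers to a separate placebo-controlled study of efficacy. The ulcer-only curve is a legitimate analysis and can stay. A supportive analysis beside it is worth adding because the error can only favour the drug and there is no control arm.

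**What to change.** Keep the ulcer-only Kaplan-Meier curve as planned. Add to section 6.4.2.1 one supportive Kaplan-Meier analysis, in FAS and PPS at Weeks 4, 12, 24 and 52, labelled as a worst-case sensitivity analysis. In it, withdrawal under the mucosal-lesion criterion of section 3.3.5.1 counts as an event on the date of the EGD that led to it, or on the withdrawal date if there was no such EGD. Report the number of these withdrawals beside the ulcer-free rate. The withdrawal criterion itself is unchanged.

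The cost is a sentence or two of text and one extra analysis. Section 3.3.5.2 already has the withdrawal date and reason recorded in the eCRF, and the planned curve already needs the EGD dates. The downside is a supportive figure equal to or less favourable than the ulcer-only rate. If few subjects leave for this reason, it will show that the planned curve is robust.
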